1. RESEARCH BACKGROUND

Please describe the purpose of your research. Provide relevant background information and briefly state your research question(s). You may provide relevant citations as necessary. (300 Word Max.)

Lesbian, bisexual, and queer-identified (LBQ) women in the United States are more likely to drink alcohol, engage in heavy alcohol use, experience alcohol-related problems and become dependent on alcohol than are heterosexual women. Although web-based PNF interventions have become popular strategies to correct misperceived norms and reduce alcohol use in other populations, lesbian and queer women constitute a hidden population not easily reached by traditional intervention efforts. This NIAAA-funded project implements and evaluates a novel, gamified, web-based PNF alcohol intervention format culturally tailored to appeal to members of the local Los Angeles lesbian and queer female community. Packaged as a digital social game about LBQ stereotypes, LezParlay features established game mechanics including co-presence, a system of points, chance-based uncertainty, and multiple feedback topics to increase appeal and remedy many of the limitations (i.e., defensiveness, reactance, and lack of attention) associated with standard web-based PNF interventions. Uniquely, to confront both social and coping antecedents of lesbians' drinking, LezParlay seeks to reduce drinking among LBQ women by providing PNF on both alcohol use and coping behaviors utilized by peers to navigate sexual minority stigma stressors.

Multiple strategies will be employed to recruit approximately 1200 lesbian, bisexual, and queer identified women residing in the United States to take part in the online LezParlay competition. Topics in the game will change from month to month and will feature stigma-coping behaviors and alcohol use, among other topics related to familiar lesbian and queer stereotypes (e.g., relationships, sex, identity, money, stress, and future plans). Over 8 monthly rounds of play, players will receive PNF on different topics and compete for cash prizes as they test the accuracy of their peer perceptions and discover how their own attitudes and behaviors compare to actual group norms. Importantly, in Round 3, when alcohol use is first assessed as a topic, a sub-sample of 500 players who report moderate drinking will be invited to participate in a LezParlay evaluation study. Participants who elect to take part in the study will be randomized to receive either PNF on alcohol use + coping behaviors, PNF on alcohol use + control topics, or PNF on control topics in subsequent rounds of the game. These study participants will be incentivized for playing remaining rounds and completing a follow-up survey about their experiences. Analysis of LezParlay efficacy will focus on longitudinal changes in alcohol use and coping behaviors associated with condition assignment and subsequent receipt of PNF among study participants. Analysis of feasibility associated with the gamified LezParlay format will focus on acceptability ratings and other feedback gathered from trial participants as well as basic application usage among the pool of players who elect to take part in the competition but do not participate in the study, and thus, are not incentivized for their completion of rounds.

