
After viewing these results screens, participants have the option of beginning the next round or being reminded to complete it later. The participant experience and sequence of screens encountered in all rounds are the same as detailed above with 2 exceptions: Rounds 3 and 4, which are intervention rounds and Rounds 7 & 8 which include REPLAY BONUSES.

Intervention Rounds 3 and 4. We aim to recruit a minimum of 1200 LBQ women to sign up during the first 2 monthly rounds to ensure that meaningful and stable sexual identity- and age group-specific actual norms for drinking and coping behaviors can be delivered in intervention rounds 3 and 4. From this larger pool of players, 500 will be recruited to participate in a LezParlay evaluation study (RCT) during Round 3. Acting as baseline (T1) for the RCT, Round 3 will feature questions about alcohol use, stigma experiences, and a group of nonhealth-related control questions submitted by players. Upon submitting answers to alcohol-related questions in Round 3, players will be covertly screened for evaluation study eligibility based on their answers (i.e., number of drinking days per week and peak drinks on a single day during the past 2 months) as well as their geolocation and the number of previous rounds played. Those who have played at least one previous round, are in the United States, and report drinking alcohol on 3 or more days per week or having 3 or more drinks on their peak drinking occasion will be invited to take part in an evaluation study at the end of the round. Interested potential participants will advance to an informed consent screen that explains that the goal of the study is to evaluate the impact and format of detailed results received in LezParlay and gather player feedback to inform the next version of the competition. The information further detailed that participation in the evaluation study simply involves playing and viewing detailed results in subsequent rounds and completing a brief feedback survey at the end of the competition. Participants can earn up to US \$40 in electronic gift cards of their choice to play subsequent rounds and complete the feedback survey. Those who check a box indicating that they understood what the study participation entails and would like to participate will be welcomed into the study.

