Qualtrics Research Suite's automated randomizer will be used to randomize evaluation study participants to a PNF condition at the point of study enrollment in round 3. Randomization will determine the sequence of topics on which participants will receive detailed results across intervention rounds 3 and 4: alcohol+coping, alcohol+control, or control only. Members of the research team will be blinded to participant condition assignment, and the study participants will not be aware that any sort of randomization was taking place. Rather, like in other rounds, when detailed results are sent players will be prompted to choose among 3 animated, graphical doors to determine the topics on which they will view detailed results. Although the results topics will be truly determined via chance in most rounds of the competition, the doors of evaluation study participants will be fixed to open to their randomly assigned feedback topics regardless of the door they selected in rounds 3 and 4. Upon completing the feedback survey at the end of the competition, participants will be debriefed regarding the study's research questions and the fixed sequences of health or control feedback they were randomized to receive in rounds 3 and 4. See Appendix D for the Debriefing Statement.

Replay Bonus Rounds 7 and 8.

The last 2 rounds of the competition, 7 & 8, will feature new question topics as well as previously assessed REPLAY BONUS topics which will allow all players to boost their scores by placing very large bets on a topic they already received feedback on and very small bets for topic on which feedback has not yet been delivered. PNF will be delivered for the new topics assessed in each round but will not be repeated for REPLAY BONUS topics. Instead a single screen will reveal the points earned from REPLAY BONUSES. Importantly, answers to REPLAY BONUS questions in Round 7 among intervention study participants' will act as the 2 month post-intervention follow-up for the purpose of the evaluation study RCT.

Competition Conclusion

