APPENDIX C

Norm questions to be featured in intervention rounds or potentially featured as control/filler questions in LezParlay Rounds

- Parallel Questions will also ask participants to report their own corresponding behavior/attitude/experience
- All questions will pipe the sexual identity (lesbian, bisexual, queer) and age-group (20s, 30s, 40s, 50s) of the user
- Some question topics and questions to appear in rounds will be voted on by players.
- Players can also submit their own questions to be voted on and potentially featured in some rounds.
- If any top voted user-submitted materially differ from those submitted in this exhaustive potential question list, we will submit an addendum to the IRB and get approval before any are featured in a round.

Alcohol Use Questions (Round 3 & Replay Bonus in Round 7)

During the past 2 months, on average, how many days per week did the Typical Lesbian drink alcohol?

- 0
- 1
- 2
- 3
- 4
- 5
- 6
- 7

During the past 2 months, on average, how many drinks did the Typical Lesbian have each time she drank?

- 0
- 1
- 2
- 3
- 4
- 5
- 6
- 7
- 8
- 9

10 or more

On the day she drank the MOST during the past 2 months, how many drinks did the Typical Lesbian have?

0

1

2

3

4

5

6

7

8

9

10

11

12 or more

HAD A HANGOVER OR ILLNESS

HAD PROBLEMS WITH FRIENDS OR FAMILY

GOT IN A PHYSICAL OR VERBAL FIGHT

PERFORMED POORLY AT WORK/SCHOOL

HAD PROBLEMS WITH GF/PARTNER

HAD PROBLEMS WITH MONEY

MISSED A SOCIAL ENGAGEMENT OR
EVENT

HAD AN UNWANTED OR REGRETTABLE
SEXUAL EXPERIENCE

During the past 2 months, how many of the 8 things above has the typical lesbian experienced due to drinking/partying?

0

1

2

3

4

5

6

7

Stigma Questions (Round 3 & Replay Bonus in Round 7)

During the past 2 months, what % of lesbians have been physically assaulted due to their sexual identity?
0% ----- 100%

During the past 2 months, what % of lesbians have been verbally harassed or threatened online or in person due to their sexual identity?
0% ----- 100%

During the past 2 months, what % of lesbians have overheard negative LGBTQ-related comments, jokes, or slurs?
0% ----- 100%

During the past 2 months, what % of lesbians have felt unwelcome or uncomfortable in a public place (gym locker room, store, restaurant, etc., due to their sexual identity?
0% ----- 100%

Coping Behaviors (Round 4)

When experiencing stress & stigma during the past month, what % of the time did the typical lesbian cope by drinking alcohol?
0% ----- 100%

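### Change in coping behaviours is a stated efficacy focus, but coping is not measured before randomisation or listed for the Round 7 follow-up, and only drinking to cope is asked again, in different words

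*Protocol*

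**What the plan says.** **Aim.** Section 1 (Research Background) states: "Analysis of LezParlay efficacy will focus on longitudinal changes in alcohol use and coping behaviors associated with condition assignment". Section 2 describes efficacy more narrowly, as reduction of alcohol use.

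**Baseline and randomisation.** Section 3 (Procedures) says: "Acting as baseline (T1) for the RCT, Round 3 will feature questions about alcohol use, stigma experiences, and a group of nonhealth-related control questions". The Qualtrics randomiser is used to "randomize evaluation study participants to a PNF condition at the point of study enrollment in round 3".

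**Order of feedback and questions.** Round 3 results are shown before Round 4 is played: "After viewing these results screens, participants have the option of beginning the next round".

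**Follow-up.** Replay answers in Round 7 "will act as the 2 month post-intervention follow-up for the purpose of the evaluation study RCT". Section 3 refers the reader to Appendix C for the intervention and replay questions.

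**Question list.** In Appendix C the alcohol heading begins "Alcohol Use Questions (Round 3 & Replay Bonus in Round 7" and the stigma heading "Stigma Questions (Round 3 & Replay Bonus in Round 7". The coping heading begins "Coping Behaviors (Round 4" and names no other round. The coping block has four behaviours (drinking, drug use, relaxation or exercise, talking to someone) and two acceptability attitudes. Each item has a parallel own-report version.

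**Final survey.** Appendix D repeats the four alcohol items and adds one coping item, drinking to cope.

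**The concern.** A longitudinal analysis by randomised condition needs each outcome at two time points at least, preferably with the first before randomisation and with the same wording at both. Alcohol has this and coping does not. Coping is first asked one round after randomisation, normally after the Round 3 feedback has been seen, and it is absent from the list for the designated follow-up.

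Coping feedback is what separates the alcohol+coping arm from the alcohol+control arm, so an effect on coping is a natural question for this trial. On the listed schedule the trial could report on drinking to cope only, yet Section 1 would lead a reader to expect results on coping behaviours in general. A statistical analysis plan cannot repair this, because analysis cannot recover answers to questions that were never asked.

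**Working it through.** **1. Own-report items by time point** (Section 3, Appendix C, Appendix D)

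| Items | Round 3 (T1, randomisation) | Round 4 | Round 7 (follow-up) | Final survey |
|---|---|---|---|---|
| Alcohol (4) | 4 | 0 | 4 | 4 |
| Coping behaviours (4) | 0 | 4 | 0 | 1 |
| Coping attitudes (2) | 0 | 2 | 0 | 0 |

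No coping item is listed for Rounds 1 and 2, and the filler list contains none.

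- Alcohol over T1, Round 7 and the survey: 4 × 3 = 12 of 12 present.
- Coping behaviours over the same three points: 1 of 4 × 3 = 12 present.
- Coping behaviours with a pre-randomisation value: 0 of 4.
- Coping behaviours with any second time point once Round 4 is counted: 1 of 4. The other 3 have one time point only. With the two attitudes included, 5 of 6 items have one time point only.

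The counts record presence, not identical wording. The alcohol items also change recall window in the survey, but they have Round 3 and Round 7 measurements under one shared wording.

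**2. The one repeated coping item**

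| | Round 4 | Final survey |
|---|---|---|
| Trigger | stress and stigma | stigma or negative emotions |
| Recall | past month | from the start of July |
| Act | coping by drinking | drinking in order to feel better |

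A change score from Round 4 to the survey mixes real change with the change of question. A comparison between arms at the survey is largely free of this, because all arms receive the same wording.

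**3. Precision of the follow-up-only comparison**

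The protocol gives N = 500 and three arms. It states no power, alpha, correlation or dropout, so these are assumptions: equal allocation, 80% power, two-sided 5%, and a baseline-to-follow-up correlation r of 0.5 to 0.7.

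Detectable difference in SD units = (1.960 + 0.842) × √(2/n) × √(1 − r²), with r = 0 when there is no baseline.

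| n per arm | No baseline | r = 0.5 | r = 0.6 | r = 0.7 |
|---|---|---|---|---|
| 500/3 = 166.7 | 0.307 | 0.266 | 0.246 | 0.219 |
| 166.7 × 0.8 = 133.3 (20% dropout) | 0.343 | 0.297 | 0.274 | 0.245 |

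Equal precision without a baseline needs 1/(1 − r²) times the sample: 1/(1 − 0.25) = 1.33 at r = 0.5 and 1/(1 − 0.49) = 1.96 at r = 0.7.

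This cost applies to contrasts with the control-only arm, before any gain from other covariates. For alcohol+coping against alcohol+control, Round 4 precedes all coping feedback and can serve as a covariate if Round 3 feedback was the same in both arms.

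**The case against.** **Round 4 is a workable baseline.** Round 3 results go out after about three weeks, a player may start Round 4 straight after seeing them, and the coping items look back one month. For a prompt player most or all of that window predates the alcohol feedback. This stands in part, and any contamination may be small. But Round 4 is still after randomisation, players may delay it or skip it, and feedback can alter how people report. Nor does it give a second time point to the three behaviours that are never repeated.

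**Section 1 does not promise change from T1.** True. Round 4 to the final survey is a longitudinal measurement of drinking to cope. It covers one behaviour and the question changes.

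**The list may be incomplete.** The final survey presents its five drinking items as a last repeat, which implies that drinking to cope was asked earlier. Section 3 also says that Rounds 7 and 8 both replay earlier topics, so a coping replay is not expressly excluded. However, the only earlier asking listed is Round 4. Appendix C calls its list exhaustive, and only Round 7 is named as the trial follow-up. If the heading is merely incomplete, it needs correcting.

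**Efficacy means alcohol.** Section 2 supports this, and it limits the consequence. Section 1 still names coping alongside alcohol as the focus of the efficacy analysis.

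**The remedy costs more than four items per time point.** This stands for Round 7: a replay topic in game format pairs each own answer with a guess and a bet.

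**Conclusion.** The concern holds. On the listed schedule, change from T1 cannot be estimated for any coping item, and no change at all can be estimated for three of the four coping behaviours. What remains valid is a randomised comparison of drinking to cope at the final survey, and the use of Round 4 as a covariate for alcohol+coping against alcohol+control, provided Round 3 feedback was the same in those two arms. Round 4 should not serve as the baseline for contrasts with control-only; the size of any bias there is unknown.

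The missing measurements matter more than the loss of precision, whose size depends on the assumed correlation and dropout. The finding rests on Appendix C being a complete list of the intervention and replay questions, as the protocol presents it. It should be fixed, but it does not threaten the alcohol outcome.

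**What to change.** 1. Ask the four own-coping behaviour items in Round 3, after evaluation-study consent and before the randomiser runs.
2. List coping as a replay topic in Round 7, as alcohol and stigma already are, with the same wording and recall window as in Round 3.
3. Use that wording for drinking to cope in the final survey.
4. Keep the Round 4 coping items for computing and feeding back norms. Use them as a covariate only for alcohol+coping against alcohol+control.

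If items cannot be added, change Section 1 so that the coping outcome is a between-arm comparison of drinking to cope at follow-up.

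**Cost.** Four own-report items in Round 3, one edited survey item, and four own-report items in Round 7, or about eight questions there if the replay keeps its paired guesses and bets. Asking consenters about coping in Round 3 gives a slight hint that coping is of interest, which weighs a little against the concealed design. The fallback costs one sentence.

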- 1) Report having had 3+ drinks on one occasion during the past 2 months OR drinking alcohol 3+ times per week during the past 2 months in response to a Round 3 Alcohol use questions
- 2) Review and Accept the Evaluation Study Informed Consent page
- 3) Have taken part in at least 1 previous round of the competition

Two questions about alcohol use in the third round of the game will act as a screening item for the Evaluation study. Specifically, participants will be quota sampled by Qualtrics in response to a Round 2 question about the maximum number of drinks consumed on one occasion during the past month. The first 150 drinkers in each age-group (i.e., 20s, 30s, 40s, 50s) who provide an answer equal to or above 3 drinks in response to this question will be invited to become an official tester in a study evaluating LezParlay. On screen text will explain that as a participant in this study they can help evaluate LezParlay by playing the next 5 rounds of the game and completing a follow-up survey about their experiences when the game is over. Further, study participants will be emailed a \$40 electronic gift card to compensate them for their time and they will still be eligible to compete for performance-based cash prizes awarded to the top scorers.

“Non-Evaluation Study participants” refer to players who register for LezParlay but either do not screen into the study or choose not to participate in the study. Non-Evaluation Study participants are not incentivized for round completion but may compete for several performance-based cash prizes awarded to the top scorers in each age-group. For these participants, LezParlay web app data analyzed for research purposes is limited to aggregated demographic data provided at registration, the number of

rounds played, number of logins, and number of screen views. Collection and analysis of this data is outlined in the web app's Terms of Service & Privacy Policy which ALL participants must review and accept at registration.

3. PROCEDURES

Summarize fully all procedures to be conducted with human subjects.

All contact with participants will occur digitally via emails, text messages, and Qualtrics surveys embedded within the LezParlay web app. All recruitment materials will link to the LezParlay website which provides information about the game and button to register. The registration survey will verify participants' geolocation in the United States, prompt participants to review and accept the LezParlay's Terms of Service & Privacy Policy, and create a unique username and password which they will use to login to the LezParlay web app. Additional registration items will ask participants to select their sexual identity (i.e., lesbian or queer), and provide their mobile phone number, email address, relationship status, birthdate and age-group. The registration survey will also present participants with the option of uploading a photo avatar to represent them within the web-app. Descriptive text will explain that if they elect to provide one, their custom avatar will be visible within the app to other logged in players. If they choose not to upload an avatar they will be represented within the app by a default blank avatar (as is done across popular social media sites and apps in the absence of a custom user avatar).

Submitting the registration form will trigger a verification text message to be sent to the mobile phone number provided by the participant. Upon receiving the text and clicking on the unique url delivered, the participant's avatar will be updated with a blue check mark and they will receive 100 Parlay Points to place bets with in Round 1. Simultaneously, verification locks the phone number so that it cannot be associated with any future LezParlay registrations and assigns a unique PIN to the participant in the registration database. As most individual's only own a single mobile phone (or 2 at the most), this protocol helps ensure that players cannot try to cheat the LezParlay system by creating multiple accounts in order to place wagers on all possible combinations of guesses. Further, the unique PIN assigned to each verified account then acts as the piece of data used by LezParlay to link participants' guesses, bets, responses, and scores across rounds of play.

Round Play- upon verification, players will be redirected to a series of instructional screens (See Appendix C) that reviews how LezParlay works and explain that points are won and lost by placing bets on your perceptions of the behaviors and attitudes of the typical LBQ woman in your age-group. In each round there will be between 1 and 3 question topics and each topic will contain approximately 8 questions. Four questions will ask you to report your own topic-specific behaviors or attitudes and the other four will ask you to guess about how other players in your age-group answered the same questions. For each guess you will be prompted to select the number of points you would like to bet on your guess being correct based on the average responses of other players. Screens will also inform participants that there is a variable cash prize between \$100 and \$500 in each round that will be awarded to the player who accumulates the largest number of points in that round. There are also grand prizes (\$1000, \$500, and \$250) that will be awarded to the top 3 scorers in each age-group who accumulate the largest numbers of points across rounds of play. A final screen will explain that after a critical mass (N=300+) in each age-group has played a round, LezParlay will text and email all players with a private link to an overview of the points won and lost along with detailed results on one topic. Detailed results are intended to help players improve the accuracy of their perceptions and place smarter bets in future rounds, as question topics may be repeated. Following this overview, a button will allow players to begin round 1.

The first screen in the round will reveal 2-3 question topics and the amount of the cash prize for the round's top scorer. Players will report their own answers to the questions then guess and bet points

(i.e., 10, 25, or 50 points) on how other players will answer. Upon placing their bets, a final screen will reiterate that results will be sent out when a critical mass has played in their age-group. Additionally, they will be informed that they can help speed this along by inviting friends to play by sharing their personalized referral link, displayed below and also available in their account tab. When a critical mass has played (>300 in each age-group which we expect to take approximately 3 weeks), average responses to questions have been computed, and points won and lost have been calculated, links to view detailed results will be sent to players via text message and email. Clicking the private url will take the player to a spinner screen which displays their total score and reveals their detailed results topic initial “RESULTS LOADING” screen which summarizes the number of players in the users’ age-group who played the round to generate the correct answers (i.e., actual norms). Consistent with co-presence features in popular social media and digital apps, this summary consists of an animated collage displays the thumbnail avatars of all the players who completed the round. Recent studies in our lab have established that showing participants the peers on whom actual norms are based through such a collage increases the believability and credibility of the actual norms to be presented on subsequent feedback screens. The next screen encountered when viewing one’s detailed results will feature 3 animated graphical doors and instructions to select (tap or click) 2 of the doors in order to reveal either bonus points or topics on which detailed results will be delivered. For each question topic revealed by the door selection mechanic, personalized normative feedback (PNF) for each question will follow. PNF consists of bar charts with bars respectively representing 1) the participant’s guess about how other players answered (i.e., perceived peer norm); 2) the participant’s own answer to the question; and, 3) the actual average answer submitted by other players (i.e., actual peer norm). Text on each PNF screen will highlight an interesting statistic related to the actual norm and detail the number of points won/lost based on the accuracy of the player’s guess. Following PNF screens, participants will be presented with their total score and their age-group’s leaderboard which also crowns the winner of the round’s cash prize. The round winner will also be notified by email and text message and have the option of receiving their Visa gift card electronically or through the mail. See Appendix B for mockups of app screens.

After viewing these results screens, participants have the option of beginning the next round or being reminded to complete it later. The participant experience and sequence of screens encountered in all rounds are the same as detailed above with 2 exceptions: Rounds 3 and 4, which are intervention rounds and Rounds 7 & 8 which include REPLAY BONUSES.

Intervention Rounds 3 and 4. We aim to recruit a minimum of 1200 LBQ women to sign up during the first 2 monthly rounds to ensure that meaningful and stable sexual identity- and age group-specific actual norms for drinking and coping behaviors can be delivered in intervention rounds 3 and 4. From this larger pool of players, 500 will be recruited to participate in a LezParlay evaluation study (RCT) during Round 3. Acting as baseline (T1) for the RCT, Round 3 will feature questions about alcohol use, stigma experiences, and a group of nonhealth-related control questions submitted by players. Upon submitting answers to alcohol-related questions in Round 3, players will be covertly screened for evaluation study eligibility based on their answers (i.e., number of drinking days per week and peak drinks on a single day during the past 2 months) as well as their geolocation and the number of previous rounds played. Those who have played at least one previous round, are in the United States, and report drinking alcohol on 3 or more days per week or having 3 or more drinks on their peak drinking occasion will be invited to take part in an evaluation study at the end of the round. Interested potential participants will advance to an informed consent screen that explains that the goal of the study is to evaluate the impact and format of detailed results received in LezParlay and gather player feedback to inform the next version of the competition. The information further detailed that participation in the evaluation study simply involves playing and viewing detailed results in subsequent rounds and completing a brief feedback survey at the end of the competition. Participants can earn up to US \$40 in electronic gift cards of their choice to play subsequent rounds and complete the feedback survey. Those who check a box indicating that they understood what the study participation entails and would like to participate will be welcomed into the study.

Qualtrics Research Suite's automated randomizer will be used to randomize evaluation study participants to a PNF condition at the point of study enrollment in round 3. Randomization will determine the sequence of topics on which participants will receive detailed results across intervention rounds 3 and 4: alcohol+coping, alcohol+control, or control only. Members of the research team will be blinded to participant condition assignment, and the study participants will not be aware that any sort of randomization was taking place. Rather, like in other rounds, when detailed results are sent players will be prompted to choose among 3 animated, graphical doors to determine the topics on which they will view detailed results. Although the results topics will be truly determined via chance in most rounds of the competition, the doors of evaluation study participants will be fixed to open to their randomly assigned feedback topics regardless of the door they selected in rounds 3 and 4. Upon completing the feedback survey at the end of the competition, participants will be debriefed regarding the study's research questions and the fixed sequences of health or control feedback they were randomized to receive in rounds 3 and 4. See Appendix D for the Debriefing Statement.

Replay Bonus Rounds 7 and 8.

The last 2 rounds of the competition, 7 & 8, will feature new question topics as well as previously assessed REPLAY BONUS topics which will allow all players to boost their scores by placing very large bets on a topic they already received feedback on and very small bets for topic on which feedback has not yet been delivered. PNF will be delivered for the new topics assessed in each round but will not be repeated for REPLAY BONUS topics. Instead a single screen will reveal the points earned from REPLAY BONUSES. Importantly, answers to REPLAY BONUS questions in Round 7 among intervention study participants' will act as the 2 month post-intervention follow-up for the purpose of the evaluation study RCT.

Competition Conclusion

Following the announcement of winners after Round 8, the LezParlay competition will be over. A special sequence of screens follow for Evaluation Study Participants. Study participants will be provided the opportunity to complete the follow-up survey for the evaluation study on screen or have the link to emailed/texted to them so that they can complete it later. Upon submitting the short follow-up survey, participants will be prompted to select a \$40 electronic gift card (Amazon, Target, Starbucks, etc.) to receive via email. A final screen will thank them for their time and debrief them about the fixed nature of the spinners that selected their detailed results topics in Rounds 3 and 4. Text will reveal that this was necessary in order to examine the perceptual and behavioral impacts of different combinations of detailed results delivered in these rounds. Questions to be featured in Intervention and Replay Bonus Rounds are presented in Appendix C. A list of potential control/filler stereotype related questions to comprise other rounds of play also follow in Appendix C. APPENDIX D also provides the Evaluation study follow-up survey and debriefing statement.

